**Document date: Thursday December 12, 2024**

## Research Approach

We will achieve our aims by having 200 non-smoking adolescents (aged 15-16) complete a laboratory study (Figure 2). During their visit, Adolescents will then be randomly assigned to watch a smoking movie that manipulates exposure to ENDS Advertisements. Attention to movie smoking will be measured using validated eye movement measures of attention. Adolescents will then complete SC-IAT task to measure how exposure to ENDS ads affected their implicit smoking expectancies and implicit normative beliefs.

## Primary Measures

**Implicit measurement of positive smoking expectancies and social normative beliefs about smoking using the SC-IAT.** A modified version of the SC-IAT will be administered before and after exposure to ENDS ads. The SC-IAT is a validated implicit association computer task that can be used to measure the associations between a visual cue (e.g., a smoking-related image) and a) personal implicit attitudes (e.g., implicit positive smoking expectancies)

and b) implicit normative evaluations (e.g., social normative beliefs about smoking). The rationale for using the implicit association tests to assess implicit attitudes and implicit normative evaluations have been described elsewhere. Adolescents will complete two phases, a personalized phase to measure their implicit positive smoking expectancies and a social phase to measure their implicit normative beliefs about smoking (Figure 3). Each trial in the personalized phase begins with the words “Things you find positive or negative ...” presented in the upper middle of the screen that stays visible for the duration of the trial. After 500 msec, adolescents are presented with a visual smoking cue and associated word or short phrase presented in the middle of the screen. The word either conveys a positive smoking expectancy (e.g., relaxation) or a negative smoking expectancy (e.g., bad mood). The labels “Positive” and ‘Negative’ are presented on opposite sides at the top right-hand and left-hand side of the screen. The task of the participant is to categorize the cue word as “positive” or “negative” by pressing the spatially-mapped keyboard key as quickly and accurately as possible. The theory is that participants will categorize the word faster if the visual cue word pairing is congruent with their smoking expectancies. For example, an individual with high positive smoking expectancies would react faster if a visual smoking cue was paired with a positive word, such as “relaxation” than a negative word, such as “bad mood.” In a control condition, neutral non-smoking images are presented instead of smoking images. Trials in the social phase are like the personalized phase with the following expectations. Trials begin with the wording “Things most people find positive or negative ...” followed by the presentation of the trial screen. The cue word will convey a positive (cool) or negative (uncool) social belief about smoking. Like above, the theory is that participants will categorize the word faster if the visual cue word pairing is congruent with their social normative beliefs about smoking. The order in which phases are completed will be counterbalanced, and experimental procedures will follow established methods. Visual smoking images and control images will be taken from the International Smoking Image database. Smoking-related images include photos of people smoking in a variety of environmental situations. Neutral images are identical but have the smoking cues removed. Positive and negative cue words will be sampled from previous research that have used similar tasks. and derived from scales that measure smoking expectancies and normative smoking beliefs designed for adolescents.

**ENDS ad and control exposure.** Immediately following the first SC-IAT,

adolescents will view a 15-minute movie clip that manipulates exposure to ENDS ads. ENDS ad exposure will be manipulated by embedding naturally occurring commercial breaks at 5 and 10 minutes. During each break, adolescents in the ENDS ad exposure condition will view ENDS ads for 30 seconds each. The commercial break will also include 3 30-sec control ads (e.g., food, clothes, and cars) to disguise the purpose of the experiment. Adolescents in the control ad condition will view 4 minutes of control commercials at each break. ENDS and control ads will be randomly sampled from the 8 most popular brands in the United States in 2016.

**Attention to dynamic smoking cues.** Dynamic smoking cues are any action that promotes or represents a smoking behavior. Selective attention is an implicit measure of cue saliency that is defined as an automatic response to attend to an environmental stimulus. Measuring eye movements to dynamic cues has been shown to be a validated measure of selective attention to smoking cues in movies. Eye tracking will be recorded using the Gazepoint GP3 eye-tracker (Vancouver, British Columbia). The GP3 device has a sample rate of 60 Hz and an accuracy of 0.5 to 1 degree of visual angle.

**Covariate Assessment.** We will measure the following covariates because they have been associated with tobacco advertising exposure and adolescent smoking, but are not thought to part of the causal pathway. We will collect sociodemographic factors including age, gender, and socioeconomic status. Socioeconomic status will be measured using the validated three item index of the Programme for International Student Assessment. We will also measure social influences on smoking using validated questions, including the smoking status of parents and the smoking status of peers. Rebelliousness and sensation seeking will be assessed using a validated 4-item index because it has been strongly associated with adolescent smoking intuition. Following our laboratory's previous work, we will also measure long-term exposure to on screen movie smoking using a validated method.

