## Primary analysis plan

Our outcomes of interest are as follows: 1) Implicit positive vaping expectancy scores measured post-intervention, and 2) selective attention to dynamic smoking cues. To assess the effect of ENDS advertising on implicit attitudes, we will use linear regression to predict Implicit positive vaping expectancy scores from advertising condition. We also use linear regression to assess the association between the amount of attention given to dynamic smoking cues and Implicit positive vaping expectancy scores. Specially, Implicit positive vaping expectancy scores will be predicted from dynamic attention scores in the onscreen smoking experimental arm. For all analyses, we will first calculate appropriate summary statistics, assess normality, and transform the data if necessary. We will include potential covariates in all analyses when they are significantly associated with the outcome ( $P < 0.05$ ). We will conduct all analyses in the full sample stratified by sex, and conduct formal tests for interactions using a Wald Test on sex by exposure multiplicative interaction terms in full models.

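### SC-IAT phase order is counterbalanced but does not appear in the planned regressions; adding it as a fixed term would be a small, nearly free gain in precision

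*Combined protocol and SAP*

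**What the plan says.** The SC-IAT "will be administered before and after exposure to ENDS ads" (Primary Measures). Each administration has a personalized phase, which measures expectancies, and a social phase, which measures normative beliefs. On their sequence the same section says: "The order in which phases are completed will be counterbalanced". It does not say how order is assigned, whether it is balanced within advertising condition, or whether a participant keeps one order for both administrations.

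For the condition effect, the Primary analysis plan states: "we will use linear regression to predict Implicit positive vaping expectancy scores from advertising condition". A second regression uses attention as predictor: "Implicit positive vaping expectancy scores will be predicted from dynamic attention scores in the onscreen smoking experimental arm". For further terms the rule is: "We will include potential covariates in all analyses when they are significantly associated with the outcome", with P < 0.05 as the threshold. The Covariate Assessment paragraph lists age, gender, socioeconomic status, parental and peer smoking, rebelliousness and sensation seeking, and long-term exposure to movie smoking. Phase order is not in that list and is named in no model.

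**The concern.** The analysed outcome is the post-intervention expectancy score, which is taken here to come from the personalized phase alone. Under counterbalancing, some participants would give that score first after the movie and others only after completing the social phase. The task is speeded, so practice, fatigue or carry-over from the social phase could shift the score. Order then varies between participants and does not cancel within a person.

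Counterbalancing keeps an order effect from being systematically tied to advertising condition. It does not take the order variance out of the residual; a term in the model does that. At stake is the width of the confidence interval for the condition effect and, to a lesser degree, power. The sex-stratified analyses and the one-arm attention regression use fewer participants, so precision is scarcer there.

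**Working it through.** **Inputs from the documents.** The total sample is 200 (Research Approach). On allocation, the same section says only: "Adolescents will then be randomly assigned to watch a smoking movie that manipulates exposure to ENDS Advertisements". The primary model is a linear regression on advertising condition.

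**Assumptions, because the documents are silent.** Allocation is 1:1, so 100 per arm. There are equal numbers in each phase order, the SD within order is 1, the test is two-sided at 5%, and there is no dropout. The order shift d runs from 0.1 to 0.8 SD. The plan states no power, effect size or SD, so it has no figure to reproduce.

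**Formulas.** A balanced two-level factor with shift d adds d²/4 to the variance.
- Share of variance due to order: (d²/4) / (1 + d²/4).
- Adjusted SE of the condition effect: √(2/100) = 0.1414.
- Unadjusted SE: 0.1414 × √(1 + d²/4).
- Power for an illustrative 0.4 SD condition effect, normal approximation: 80.7% with the adjusted SE. The last column of the table uses the unadjusted SE.

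| d | Variance share | Unadjusted SE | Excess over adjusted SE | Power at 0.4 SD |
|---|---|---|---|---|
| 0.1 | 0.25% | 0.1416 | 0.1% | 0.8065 |
| 0.2 | 1.0% | 0.1421 | 0.5% | 0.8036 |
| 0.3 | 2.2% | 0.1430 | 1.1% | 0.7988 |
| 0.5 | 5.9% | 0.1458 | 3.1% | 0.7835 |
| 0.8 | 13.8% | 0.1523 | 7.7% | 0.7473 |

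Example for d = 0.5: √(1 + 0.25/4) = √1.0625 = 1.031, and 0.1414 × 1.031 = 0.1458.

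The sample-size equivalent is the number of extra participants that an unadjusted analysis would need to match the adjusted one, 200 × d²/4. That is 0.5, 2, 4.5, 12.5 and 32 across the five rows.

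**Does the unadjusted SE describe the real sampling error?** This depends on how order is assigned. A simulation with 200 participants, 20,000 replicates and no condition effect compared the model SE of the unadjusted regression with the empirical SE of its estimate.

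| d | Order assignment | Model SE | Empirical SE | Type I error |
|---|---|---|---|---|
| 0.2 | Balanced within arm | 0.1419 | 0.1422 | 5.0% |
| 0.5 | Balanced within arm | 0.1456 | 0.1409 | 4.3% |
| 0.8 | Balanced within arm | 0.1523 | 0.1427 | 3.6% |
| 0.2 | Independent of arm | 0.1420 | 0.1426 | 5.2% |
| 0.5 | Independent of arm | 0.1455 | 0.1452 | 4.9% |
| 0.8 | Independent of arm | 0.1523 | 0.1520 | 4.9% |

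The mean estimate was within 0.003 SD of zero in every run, so there is no sign of bias. With balance within arm, the estimate is as precise as the adjusted one, but the model reports a larger SE, so the test is conservative. With independent assignment, the reported SE is correct and the estimate itself is less precise. With the order term in the model, type I error was between 4.9% and 5.2% throughout.

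**The case against.** The strongest counter-argument is that this is a refinement. Counterbalancing already protects the comparison from order bias, no order effect is documented, and the loss is negligible at small shifts. The task compares positive with negative words and has a neutral-image control condition, so a general change in speed could largely cancel in the score. The scoring formula is not given, so shifts of 0.5 to 0.8 SD are only the upper end of an assumed range. All of this stands, and it keeps the point minor.

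It can also be said that order might enter as a potential covariate under the P < 0.05 rule. Nothing in the text makes it a candidate. If it were one, the rule would select it with probability of about 11%, 29%, 56%, 94% and nearly 100% at shifts of 0.1, 0.2, 0.3, 0.5 and 0.8 SD. The rule would thus catch the large effects, but at moderate ones a factor fixed by the design would enter or leave by chance.

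A reader might infer that the planned standard errors are simply too wide. The documents do not support that. It needs both a real order effect and order balanced within advertising condition, and neither is stated. Nor does the argument carry over to the attention regression: order is not balanced against a measured attention score, so at most some precision is lost there. A reader might also infer that chance imbalance in order between arms biases the result. Under independent assignment such imbalance is ordinary sampling error, which the unadjusted SE already covers.

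**Conclusion.** The point holds as a minor gap between design and analysis. Order is controlled by the design and then unused, so any order effect stays in the residual of the expectancy models. The validity of the condition comparison is not in question, provided order is not systematically tied to advertising condition.

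The cost in standard error is about 1% or less for order shifts up to 0.3 SD, about 3% at 0.5 SD and about 8% at 0.8 SD. For an illustrative 0.4 SD condition effect, the last of these takes power from 80.7% to 74.7% when order is assigned independently of arm. These figures rest on 1:1 allocation, equal numbers in each order, order that differs between participants at the post-exposure task, and assumed order effects. The true order effect may be close to zero, in which case nothing is lost either way. No figure is offered for the attention regression, because it was not part of the calculation.

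**What to change.** State in Primary Measures that phase order is balanced within each advertising condition and that each participant's assigned order is recorded at both administrations. In the Primary analysis plan, add one sentence: the order at the analysed administration enters as a fixed term in every regression with an SC-IAT score as outcome, including the attention and sex-stratified models, regardless of its P value and outside the covariate screen.

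The cost is one degree of freedom per model, for example 197 instead of 198 residual degrees of freedom in the two-arm regression without other covariates (200 − 3 instead of 200 − 2). No extra participants or visits are needed.

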## Primary analysis plan

Our outcomes of interest are as follows: 1) Implicit positive vaping expectancy scores measured post-intervention, and 2) selective attention to dynamic smoking cues. To assess the effect of ENDS advertising on implicit attitudes, we will use linear regression to predict Implicit positive vaping expectancy scores from advertising condition. We also use linear regression to assess the association between the amount of attention given to dynamic smoking cues and Implicit positive vaping expectancy scores. Specially, Implicit positive vaping expectancy scores will be predicted from dynamic attention scores in the onscreen smoking experimental arm. For all analyses, we will first calculate appropriate summary statistics, assess normality, and transform the data if necessary. We will include potential covariates in all analyses when they are significantly associated with the outcome ( $P < 0.05$ ). We will conduct all analyses in the full sample stratified by sex, and conduct formal tests for interactions using a Wald Test on sex by exposure multiplicative interaction terms in full models.

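### The effect of ENDS ads on implicit normative beliefs is a stated purpose and a primary measure, but the analysis plan has no model for it

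*Combined protocol and SAP*

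**What the plan says.** The Research Approach gives the SC-IAT two targets: it is used "to measure how exposure to ENDS ads affected their implicit smoking expectancies and implicit normative beliefs". Primary Measures says the task "will be administered before and after exposure to ENDS ads". It separates what the task yields into "personal implicit attitudes (e.g., implicit positive smoking expectancies)", measured in a personalized phase, and "implicit normative evaluations (e.g., social normative beliefs about smoking)", measured in a social phase with its own prompt and cue words.

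The Primary analysis plan lists two outcomes: "Our outcomes of interest are as follows: 1) Implicit positive vaping expectancy scores measured post-intervention, and 2) selective attention to dynamic smoking cues". It then specifies two regressions:

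- The randomised comparison: "we will use linear regression to predict Implicit positive vaping expectancy scores from advertising condition".
- The attention model: "Implicit positive vaping expectancy scores will be predicted from dynamic attention scores in the onscreen smoking experimental arm".

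The rest of that section covers summary statistics, transformation, covariates, stratification by sex, and a plan to "conduct formal tests for interactions using a Wald Test on sex by exposure multiplicative interaction terms in full models". These sentences modify the analyses already named and introduce no further dependent variable.

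**The concern.** A study that randomises ad exposure and scores normative beliefs before and after it should say how that score will be compared between arms. Here the construct and its measure are fixed in advance, but the comparison is not. An analyst who follows the plan produces no randomised estimate for one of the two purposes in the Research Approach. An analyst who reports one anyway has to choose its form (post-exposure score only, baseline-adjusted, or change from baseline) with the data in hand, and the nominal 5% error rate no longer holds.

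Two wording problems sit beside this. The only between-arm model is for a vaping expectancy score, whereas the measurement sections describe smoking images, smoking words and a smoking expectancy score. And attention is called an outcome but is used only to predict expectancy.

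**Working it through.** **Matching purposes, measures and models.** The plan gives no figure to reproduce on this point, so the main check is to set the sections side by side.

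| Variable | Purpose in Research Approach | Under Primary Measures | Listed outcome | Role in the two regressions |
|---|---|---|---|---|
| Expectancy score | yes (smoking) | yes (smoking) | yes (vaping) | dependent variable in 2 of 2 |
| Normative-belief score | yes | yes, social phase, before and after | no | none in either |
| Attention | measured; no ad effect stated as a purpose | yes | yes | predictor in 1 of 2, dependent variable in 0 |

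If vaping expectancy and smoking expectancy are the same score, 1 of the 2 purposes has a between-arm model. Read literally, the count is 0 of 2. The normative-belief row is the same either way.

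**Cost of leaving the form open.** Inputs: 200 participants (Research Approach). Assumed, because the documents do not state them: 100 per arm, two-sided 0.05, bivariate normal pre and post scores with correlation r of 0.3, 0.5 or 0.7. With no ad effect and 200,000 simulated trials per r, the proportion with at least one P < 0.05 is:

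| r | One pre-stated model | Post-only or baseline-adjusted | Those two or change score |
|---|---|---|---|
| 0.3 | about 5% | 6.3% | 9.1% |
| 0.5 | about 5% | 7.2% | 9.5% |
| 0.7 | about 5% | 8.3% | 10.1% |

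Each single analysis alone gave 4.9 to 5.1%.

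**Can the added model be informative?** The detectable difference at 80% power, in SD units, comes from the noncentral t distribution. The standard error is √(2/100) = 0.1414 unadjusted, and 0.1414 × √(1 − r²) after adjustment for the pre-exposure score.

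- Unadjusted, 198 df: 0.398.
- Adjusted, 197 df: 0.398 × 0.954 = 0.380 at r = 0.3; 0.398 × 0.866 = 0.345 at r = 0.5; 0.398 × 0.714 = 0.284 at r = 0.7.
- At a two-sided 0.025 level: 0.439 unadjusted; 0.439 × 0.866 = 0.380 at r = 0.5.

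The same figures apply to the expectancy model.

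**The case against.** **The analysis plan announces its first model as one for implicit attitudes, which might cover both SC-IAT scores.** It does not. Primary Measures reserves attitudes for the personal expectancies and uses a separate term, normative evaluations, for the social phase. The sentence itself predicts only the expectancy score.

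**The section is headed as the primary analysis plan, so normative beliefs may have been left out on purpose, to be secondary or exploratory.** This is possible, and the sponsor may give them that status. But the measure stands under Primary Measures, the Research Approach still states the purpose, and no other analysis section is visible. A secondary comparison also needs a stated model.

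**The 9 to 10% rate is a worst case.** This stands. No section mentions a change score, and the expectancy model offers an obvious template for its sibling score. The 6 to 8% range is the fairer figure, with 9 to 10% as an upper bound.

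**A reader might infer that the effect of ads on attention is also a study question left without an analysis.** The documents do not support this. No visible section makes that effect a purpose. Attention is listed as an outcome and modelled as a predictor, a mismatch that relabelling can settle. The arm named in that model matches neither the ENDS-ad nor the control-ad condition, but Figure 2 is not shown in the available copy and may explain it.

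**Conclusion.** The point holds for normative beliefs. A stated purpose, with its own task phase scored before and after exposure, has no planned randomised estimate. That rests on the text alone and needs no assumption beyond the limits of the public copy, which lacks Figure 2 and one removed portion.

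The size is moderate. If the form is left open, the error rate for that one score is about 6 to 8%, and at most about 9 to 10%, under the assumed correlations and equal arms.

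A reader might infer that the planned expectancy comparison is invalid. It is not: regressing a post-exposure score on randomised condition is a legitimate analysis. What cannot yet be said is that it serves the smoking-expectancy purpose, because the plan calls the score vaping and no visible section describes a vaping SC-IAT. The names must be reconciled first. The attention mismatch is a wording matter. This should be fixed before analysis.

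**What to change.** In the Primary analysis plan:

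1. Add a linear regression of the post-exposure social-phase SC-IAT score on advertising condition, adjusted for the pre-exposure social-phase score. Label it primary or secondary, as the sponsor chooses.
2. Adjust the expectancy model for its own pre-exposure score, so that both scores are analysed alike. Under the assumptions above, its detectable difference falls from 0.40 SD to 0.38, 0.345 or 0.28 SD at correlation 0.3, 0.5 or 0.7.
3. Use one name for the expectancy score, smoking or vaping, that matches the SC-IAT described under Primary Measures.
4. Call attention a predictor. If it is to stay an outcome, add a regression of attention on advertising condition, using only movie footage after the first break and excluding all commercial time. In either case, name the arm or arms used in the attention-expectancy model.

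The cost is wording plus one added regression (two if attention stays an outcome), on scores the plan already collects. Because the plan attaches sex stratification and an interaction test to all analyses, the normative-belief model brings two sex-specific estimates and one interaction test, besides any pooled estimate. If the sponsor tests the added comparison at 0.025, its detectable difference rises from 0.345 to 0.38 SD at correlation 0.5.

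### No primary test is named among two regressions and their sex-specific repeats, and attention, though listed as an outcome, is never compared between the randomised arms

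*Combined protocol and SAP*

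**What the plan says.** All of this comes from the section *Primary analysis plan*.

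- Two outcomes are listed, with neither named as the main one: "Our outcomes of interest are as follows: 1) Implicit positive vaping expectancy scores measured post-intervention, and 2) selective attention to dynamic smoking cues".
- First regression: "we will use linear regression to predict Implicit positive vaping expectancy scores from advertising condition". This is the randomised comparison.
- Second regression: "We also use linear regression to assess the association between the amount of attention given to dynamic smoking cues" and the expectancy score. The model is specified as follows: "Implicit positive vaping expectancy scores will be predicted from dynamic attention scores in the onscreen smoking experimental arm". Attention is on the right-hand side.
- Sex: "We will conduct all analyses in the full sample stratified by sex". The plan will also "conduct formal tests for interactions using a Wald Test on sex by exposure multiplicative interaction terms in full models".
- The only threshold in the document belongs to a covariate rule: "We will include potential covariates in all analyses when they are significantly associated with the outcome", with P < 0.05. It is not a level for the hypothesis tests.

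The document contains no testing order, no multiplicity adjustment, no statement that the sex analyses are exploratory, and no sample-size or power calculation. *Research Approach* gives only the total of 200 participants.

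**The concern.** There are two linked problems.

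First, the plan does not say which result answers the trial's question. A randomised contrast and a within-arm association stand under the same heading, and each can be reported overall, in girls, in boys and as an interaction. If several of these are tested without order or correction, whichever turns out significant can be presented afterwards as the main finding, at an error rate above the level of any single test. The association is also weaker evidence: adolescents are not randomised to how much they look at smoking cues, so a significant slope within one arm is open to confounding and says nothing about the effect of the advertisements.

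Second, attention is declared an outcome, but no planned model has it as the dependent variable. Randomisation would support a direct comparison of attention between advertising conditions, and the plan does not make it.

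**Working it through.** The plan states no error rate, so there is no figure of its own to reproduce. The check asks how large the family-wise error would be under each plausible reading.

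**Inputs from the document.** Two regressions; up to four tests in each (overall, girls, boys, sex interaction); 200 participants.

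**Assumptions.** Two-sided 0.05 per test, all null hypotheses true, no adjustment, sexes split 50/50. The arm named for the second regression is taken to be one of the two randomised arms, because the rest of the document describes only ENDS-advertisement and control-advertisement conditions.

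**Dependence within one regression.** Let z_m and z_f be the independent statistics for boys and girls, and p the proportion of boys.
- Overall: z_o = √p·z_m + √(1−p)·z_f
- Interaction: z_i = √(1−p)·z_m − √p·z_f

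The covariance of z_o and z_i is √p·√(1−p) − √(1−p)·√p = 0, so these two are independent of each other. The stratum tests overlap with both, so the wider readings were simulated (2,000,000 draws).

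**Two regressions together.** If f is the error for one regression, the error for both, treated as independent, is 1 − (1 − f)².

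| Tests counted in each regression | f | Both regressions |
|---|---|---|
| Overall only | 0.05 | 1 − 0.95² = 9.75% |
| Overall and interaction | 1 − 0.95² = 0.0975 | 1 − 0.95⁴ = 18.5% |
| Overall and both strata | 0.115 | 1 − 0.885² = 21.7% |
| Both strata and interaction | 0.115 | 1 − 0.885² = 21.7% |
| All four | 0.1326 | 1 − 0.8674² = 24.8% |

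**Sensitivity.** For all eight tests the result is 24.6% at a 60/40 sex split and 24.3% at 70/30. Treating all eight as independent would give 1 − 0.95⁸ = 33.7%, which is too high because the tests overlap.

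**Check on independence between regressions.** A full least-squares simulation used 20,000 trials, 200 participants, an assumed 100 per arm and half of each sex, with the second regression run in one arm of 100. It gave 24.7% for all eight tests and 9.7% for the two overall tests. Treating the regressions as independent is therefore adequate here.

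**Role of attention.** Set side by side, the outcome list includes attention, while both model statements have expectancy as the quantity predicted. No sentence predicts attention from condition.

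**The case against.** The strongest reply is that this is a small laboratory study in which sex analyses are usually read as exploratory. It adds that the plan lists expectancy first and distinguishes the two regressions in kind, calling one an effect and the other an association. That is fair as far as it goes. The document does not say that a single-sex or interaction result would be taken as the main conclusion. It also mentions aims that the available text does not set out. But the order of a list is not a testing hierarchy, and nothing in the text gives the sex analyses exploratory status; they are applied to every analysis under a heading that calls the plan primary.

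A reader might also infer more than the document supports, in three ways.

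- *That every test is planned at 0.05.* The only 0.05 is the covariate rule. The level used above is an assumption.
- *That the false-positive risk is simply one in four.* That figure needs the widest reading of an ambiguous sentence about the full sample and sex strata, with all eight tests able to supply the main finding. Narrower readings give 10% to 22%.
- *That two outcomes are both tested.* Both regressions model expectancy. A third regression, with attention as dependent variable, would take the figure to about 35%, but the plan contains no such regression, so that figure does not describe it.

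It is also right that naming one test does not by itself secure 5%. Covariates are chosen by significance and transformation is left to the data, and the figures above leave out any inflation from either.

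**Conclusion.** The point holds in a limited form. As written, the plan names no primary test, order or adjustment, and gives a listed outcome no randomised comparison. Assuming two-sided 0.05 per test and all nulls true, the chance of at least one false positive is about 10% (two overall tests), 19% (overall plus interaction), 22% (overall plus strata, or strata plus interaction) or 25% (all eight). Even the narrowest of these readings is about twice the assumed level. Which figure applies cannot be settled from the document, so the range should be quoted rather than its upper end. This is a weakness in how results may be claimed, not an error that invalidates the randomised comparison, and it is cheap to put right.

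**What to change.** In *Primary analysis plan*, state the following.

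1. The single primary test is the full-sample regression of the post-intervention expectancy score on advertising condition, two-sided 0.05.
2. Attention is regressed on advertising condition in the full sample and tested at 0.05 only if the first test is significant.
3. The within-arm association between attention and expectancy, and all sex-specific and interaction results, are secondary: estimates with 95% confidence intervals and no confirmatory claim.
4. The covariates and any transformation for the primary model are fixed in advance; the 5% level presumes this.

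The fixed order keeps the confirmatory error at 5%. If the first null is true, any false claim requires a false positive at step one (5%); if it is false, only step two can err (at most 5%).

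The cost is one added regression on data already collected, plus wording. The primary test loses no power, since it keeps the full assumed 0.05. The downside is that an isolated attention, association or single-sex result can no longer be called confirmatory. One related point must be settled for the primary test to be fully defined: *Primary Measures* describes smoking expectancies, whereas the analysis section names vaping expectancies, and the score should be identified.
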